Using the data from our retrospective review of outcomes following labral repair, a 10 point or greater difference on the mHHS as significant, and a single-tail independent t-test to evaluate the difference between means with 80% power and a 5% significance level, 35 subjects are needed to demonstrate a statistically significant difference between the average mHHS of the conservative group and surgical group. Testing of hypothesis 1.5 will be an intragroup analysis looking for a significant difference in outcome measures from the time of completion of PT (non-crossover) when compared to the same data to be collected at 12 months and 24 months. The purpose is to determine the short-term durability of the response to PT, if one is found.

70 study completers should provide us with the necessary data needed to substantiate or reject our hypothesis. There has been no prospective trial to date testing these hypotheses in the hip, but we expected a 7.3-10.3% dropout rate based on the results of a similar study in the knee. However, as of July 2018, we had 47 patients that had passed the 2-year follow-up mark, of which 5 patients were no longer in the study (combination of lost to follow-up and proceeding to total hip arthroplasty), and another 11 had yet to complete their 2-year surveys even with multiple attempts to contact them and encourage them to do so. With a yield of 31 patients out of 47, or 65.95%, we increased our sample size to 122.

Therefore, we estimate needing 122 subjects to achieve 70 study completers, in the appropriate proportion of 35 subjects per treatment arm. We enroll until reaching at least 35 subjects in each group.

The results of the MeTeOR trial in the knee show that we can expect a higher drop-out rate in the surgical group. As such, this cohort may be our limiting factor.^{40, 43, 61, 62}

Specific Aim 2. Hypotheses 2.1-2.3: *To evaluate the significance of arthritic burden on short term outcomes following arthroscopic labral repair.*

Hypothesis 2.1 was powered on the basis of our prior work where 33% of study participants had grade 4 Outerbridge changes the time of arthroscopy. Dividing our cohort into two subgroups: 1) Those with grade 4 changes and 2) Those without. We will need 12 subjects with grade 4 changes in order to perform adequate sub-group analysis.⁶³ Powered to 80% and 5% significance level. Hypothesis 2.2 is another sub-group analysis that will be conducted in a similar fashion to that of hypothesis 2.1. However, the two groups will be categorized into: 1) cartilage defects at or near the chondro-labral junction and 2) cartilage defects not at or near the chondro-labral junction. We cannot control the heterogeneity of the subjects enrolled, but based on this analysis we expect to meet our target enrollment. Hypothesis 2.3 will be analyzed via linear regression and is appropriately powered.

Specific Aim 3 is exploratory. Since we are recruiting subjects for the main purposes of determining outcomes, we recognize that we may be underpowered for the definitive analyses of our radiographic correlation hypotheses. Nevertheless, we anticipate that we will enroll sufficient numbers of subjects to draw an association or at the very least, trend patient outcomes with degree of joint space narrowing, Kellgren-Lawrence grading, and Tonnis grading. There should also be sufficient numbers to preliminarily assess any correlations between pre-operative Kellgren-Lawrence and Tonnis grades with the Outerbridge classification at the time of arthroscopy.

VI. RISKS & DISCOMFORTS

Conservative Treatment: Subjects can expect the routine discomfort associated with any therapeutic procedure. Complications may include muscle soreness, pain, and increased edema or muscle fatigue.

Operative treatment: Since surgery is not considered a research procedure (only the randomization into the surgery group is considered a research procedure, as explained above) surgical risks are explained in the surgical consent process.

In the rehabilitation period, patients will be subject to the same potentials discomforts as those subjects in the conservative treatment group as the physical therapy protocols for both groups are identical. In both treatment groups every effort will be made to minimize the risk of adverse events and patient discomfort.

VII. POTENTIAL BENEFITS:

It is very likely that some of the subjects will derive direct benefit from participation in the study, such as improvements in pain and physical function. Outside of the estimated physical benefits from a surgical treatment or rehabilitation program, subjects may experience the monetary benefits in the forms of less missed work and increased productivity. There may also be the emotional benefit of being able to return to the normal activities of daily with a reduction in pain or no pain at all. Subjects who wish to continue their treatments at the conclusion of the study will be given the opportunity to do so through the Brigham Orthopedic Associates. It is anticipated that findings from these studies will help advance research in labral repair and patient outcomes in general. We also hope to derive a strong sense for the type of

patient age 40 and older who will benefit the most from either arthroscopic labral repair or physical therapy.

VIII. MONITORING AND QUALITY ASSURANCE:

The P.I., [name], will oversee all data collection and ensure that data are collected and stored in a confidential manner consistent with all regulatory requirements.. This study will be approved by the Partners IRB, and any protocol deviations and/or adverse events will be reported in accordance with the Partners Human Research Policy. Research assistants will be trained to identify and to bring to the research team any complaints or adverse reactions among participants. Training will include appropriate steps to alleviate or remedy common problems. [name] will have contact with staff to monitor patient participation and any issues that emerge during the protocol, and will review and discuss human subjects' protection issues with staff as unique situations emerge during the progress of the study. [name] will meet with the research team regularly for a formal research meeting. Subjects will be given telephone numbers to contact the PI and the IRB to communicate any concerns that may rise during their participation in the protocol. Please see below for specifics.

1. The study staff will meet regularly with [name] to review study participants and the data that has been collected on them to date. If a subject becomes disqualified or must leave the study for safety concerns, [name] will personally inform them of the situation through the subjects preferred method of contact. [name] will be leading and administering the conservative arm of the study (subjects being treated non-surgically with physical therapy and subjects in the post-operative period receiving rehabilitative physical therapy). She will inform [name] of patient progress and any potential clinically significant events that may warrant further discussion and could ultimately result in the dismissal of a patient from the study.
 - a. As this is a prospective study comparing the gold standard of treatment (labral repair) to a potentially equivalent therapeutic modality, qualifying subjects will never be denied the option to undergo labral repair via hip arthroscopy. The treatment schema allows for subjects in the non-surgical arm (physical therapy alone) to cross over to the surgical treatment group at any time (following physical therapy) from initial enrollment if they wish to do so. Subjects who decide to crossover or are indicated to crossover through the non achievement of advancement criteria will have the PT discontinued at that time point but must wait for official crossover at 6 weeks after initial enrollment. Participants can always decide to leave the study if this is not what they want. The decision to cross over will in no way affect the quality of healthcare current or prior study participants receive. All of this will also be explained to them during the consent.
 - b. We will review all data continuously and should there be a obvious clinical detriment to specific treatment arm such as repeated poor outcomes or worsening function, further investigation will be initiated to determine if this is an isolated occurrence or if there is a significant trend which warrants cessation of study protocol and disenrollment of subjects.
 - i. Stopping rules include a clear difference in morbidity, as measured by interval physical exams and outcomes questionnaires, between treatment groups
 - ii. Any significant mortality possibly linked to study procedures will result in immediate suspension of the study protocol.
2. A data safety monitoring board (DSMB) or data monitoring committee (DMC) is not required for the purposes of this study because large numbers of subjects will not be used in this investigation, there are no blinded treatment study groups, we are not using multiple clinical sites (all are within Partners network), we are not using high risk interventions (hip arthroscopy has been shown to be a safe option for managing intra-articular and periarthritis pathology of the hip;

physical therapy is low risk), we are not performing a controlled trial in which major morbidity or mortality are considered primary or secondary endpoints.

Adverse Events Reporting and Assessment:

Any protocol deviations and/or adverse events will be systematically documented and reported to the IRB. Adverse Event Reports and/or Case Report Forms will identify study participants by their initials and a unique study participant identifier.:.

Severity grading scale:

Mild: adverse event of little clinical significance

Moderate: adverse event between mild and severe - causing some limitation of usual activities

Severe: adverse event that results in death, is life-threatening, requires or prolongs hospitalization, causes persistent or significant disability/incapacity, represents a significant overdose or breach of protocol, results in congenital anomalies/birth defects or produces cancer, or in the opinion of the investigator, represents other significant hazards or potentially serious harm to the research subject or others.

Attribution scale:

Not related: clearly NOT related to the study

Possible: may be related to the study

Probable: likely related to the study

Definite: clearly related to the study

Unable to assess

Any serious or unexpected adverse events will be reported to the IRB within the required timeframe, using the appropriate forms. The principal investigator will provide an interim report of all adverse events to the IRB at the time of continuing review. Although this proposed project is perceived to be relatively low-risk, the study may be terminated if the frequency of serious or unexpected adverse events is higher than that anticipated. Once this determination is made, a memo will be sent to the IRB explaining the reasons for the determination. For suspended studies, an action plan will be devised which will outline what evidence and/or conditions will be required to terminate or re-initiate the study.

Reporting Unanticipated Problems including Adverse Events

The principal investigator will report to the PHRC any unanticipated problems and adverse events that occur: 1) during the conduct of the study, 2) after study completion, 3) after subject withdrawal or completion. The reports will be submitted according to PHRC policy within 5 working days or 7 calendar days of the date the investigator first becomes aware of the problem.

Subject Confidentiality:

Precautions will be taken when contacting and communicating with subjects to ensure that their participation is kept confidential. Subjects will be assured that their decision to participate will not affect their medical treatment. Throughout the study, investigators will be alert to any complaints or adverse reactions and will take appropriate steps to alleviate the difficulties as soon as possible. Subjects will be given the names and phone numbers of individuals to contact in the event of an emergency or a complaint or question regarding the conduct of the study.

All data for presentation will be identified by a code number only. Prior to releasing data to the scientific community, all data will be de-identified. Explicit permission to share the de-identified data with the scientific community will be obtained as part of the Informed Consent procedures.

Safeguarding Specimens, Records, and Data:

All research materials are obtained directly from the participants by trained and supervised study staff. All study staff who interact with human subjects have completed the requisite training in research ethics and procedures, and are approved by the institution's IRB. Each participant in the study will be assigned a study ID number as a unique identifier. All records and research data will be kept in locked filing cabinets and on password-protected, secure computer systems. Databases that link Personal Health Information with research data will be kept on secure, Partners computer systems. Only summaries of group data will be reported in any publications or presentations, with no identification of individual.

IX. REFERENCES

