Determining which patients, using age and arthritic burden as predictors, can benefit from labral repair is paramount for several reasons. Showing arthroscopic repair is of little or no benefit to a specific cohort can reduce the number of unnecessary surgeries performed, increase the use of conservative therapy (if validated) and reduce the interval between diagnosis and total hip replacement. Additionally, proving a benefit exists from arthroscopic repair in a certain subset of the population will substantiate the need for developing a treatment algorithm in older patients presenting with labral tears and some degree of pre-existing arthritis. Furthermore, conservative physical therapy may prove to be of equal or greater benefit than arthroscopic repair in select patients. If true, this study will be a landmark for providing the evidence needed to recommend conservative treatment as an efficacious alternative in addition to providing a foundation for future research on this topic.

II. SPECIFIC AIMS:

Specific Aim 1: To evaluate if physical therapy alone or arthroscopic labral repair and physical therapy is of greater benefit to patients presenting at age 40 with tears of the acetabular labrum.

Hypothesis 1.1: Physical therapy will result in a significant difference in mHHS scoring at 12 months when compared to baseline.

Hypothesis 1.2: Arthroscopic labral repair will result in a significant difference in mHHS scoring at 12 months when compared to baseline.

Hypothesis 1.3: Arthroscopic labral repair and physical therapy will be superior to physical therapy alone in improving function and alleviating symptoms at 12 months when compared to baseline, as judged by the mHHS.

Hypothesis 1.4: Hypotheses 1.1-1.3 will hold true at 24 months and beyond.

Hypothesis 1.5: Functional outcome scores collected at the completion of PT will not significantly differ from those collected at 12 and 24 months and beyond in the same group.

Specific Aim 2: To evaluate the effect of arthritic burden on short term outcomes following arthroscopic labral repair.

Hypothesis 2.1: In the surgical treatment group, subjects with arthroscopically proven severe osteoarthritis (Outerbridge grade 4) will do more poorly on validated outcome measures, specifically the mHHS, after arthroscopy than subjects with less severe osteoarthritis (Outerbridge grade ≤ 3).

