Hypothesis 2.2: Cartilage defects at or near the chondrolabral junction are prognostic indicators of worse outcomes as determined by the mHHS.

Hypothesis 2.3: Subjects with any degree of joint space narrowing (classified by Tonnis and Kellgren-Lawrence grading, see below) on plain radiographs will have more pain, regain less function, and do more poorly based on validated outcome measures, specifically the mHHS, at 6 and 12 months than subjects without any degree of joint space narrowing on plain radiographs.

EXPLORATORY Specific Aim 3: To evaluate the relationship between joint space narrowing on plain radiography and arthroscopically proven osteoarthritis.

Hypothesis 3.1: Tonnis grading and Kellgren-Lawrence grading on plain radiography are not predictive of the severity of arthritis at the time of arthroscopy.

Specific Aim 4: To analyze the data of subjects crossing over from PT alone to PT and surgery.

Hypothesis 4.1: Primary outcome scoring (mHHS) at 12 and 24 months after cross to surgery and PT will differ significantly from those initially randomized to surgical treatment.

Hypothesis 4.2: Baseline scores on outcome measures of those subjects crossing over will not differ significantly from those obtained at the time of crossover.

III. SUBJECT SELECTION & ENROLLMENT:

Study Overview: This is a prospective randomized control trial (RCT), which will enroll subjects with a clinically diagnosed tear of the acetabular labrum. Subjects who have been diagnosed with a labral tear in clinic will receive conservative physical therapy treatment alone or arthroscopic surgical labral repair and physical therapy. If it is discovered that there is unexpected pathology at the time of arthroscopy for subjects in the surgery group, those subjects will be removed from the study. This is due to the possibility that the source of pain is less likely a result of the dysfunction of the labrum and more likely due to aberrant extra-articular biology. We will use validated outcomes measures that include the mHHS, LEFS, HOS, NAHS, and iHOT-33 (see below) and review the medical record for physical exam findings to track patient progress throughout their involvement in the study which will continue for as long as they are a patient of the PI. Study procedures will be complete when the last enrolled subject completes 24-month follow-up and completes the corresponding surveys.

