The mean outcome scores of the mHHS in each treatment group at 12 months will be compared to baseline scores to assess for significant differences using paired sample t-test in SPSS 16 (SPSS, Chicago, IL). The mean outcomes scores of the mHHS between groups at 12 months will be compared using independent t-tests to assess for significant difference. We will use a Levene test to judge variance and proceed accordingly. If a statistically significant difference is detected during these analyses, we will calculate the effect size (ES) to determine how meaningful these results are outside of being statistically significant. The ES will be calculated by: [(mean mHHS score of surgical arm / mean mHHS of the conservative group) / standard deviation of the conservative group]. According to Cohen ⁵⁸, an ES <0.1 is trivial, ES of 0.1-0.3 is minimal, ES of 0.3-0.5, is moderate, and ES >0.5 is large. We will repeat the same analysis at 12 months.

Hypothesis 2.1, 2.2, and 2.3:

Diagnosis and treatment of the prearthritic and early arthritic hip has been an area of intense interest. However, our most conventional method of assessment (plain radiography) does not provide us with enough diagnostic sensitivity.⁴¹ Direct visualization on the articular surfaces in the hip is both sensitive and specific. Furthermore, emphasis is being placed on the location of arthritis as a prognostic indicator of good outcomes following hip arthroscopy. The value of arthroscopic techniques for primary

symptoms and/or prevention of OA secondary to labral tears remains unclear even though preliminary reports indicate there may be some benefit to repairing a torn labrum, even in cases of severe OA. Evaluation of arthritic change at the time of arthroscopy is important, particularly in subjects where there remains uncertainty about the efficacy of labral repair for those with articular or rim cartilage degeneration that the effects of those changes on long-term OA progression.⁵⁹

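### Hypotheses 1.1 and 1.2 claim a treatment effect, but each is tested only by a within-arm paired t-test that cannot attribute the change to treatment

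*Combined protocol and SAP*

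**What the plan says.** Section II (Specific Aims) lists two within-arm hypotheses ahead of the comparative one. Hypothesis 1.1 reads "Physical therapy will result in a significant difference in mHHS scoring at 12 months when compared to baseline". Hypothesis 1.2 reads "Arthroscopic labral repair will result in a significant difference in mHHS scoring at 12 months when compared to baseline". Hypothesis 1.3 is the comparison between arms, and Hypothesis 1.4 extends all three to 24 months and later.

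Section V (Hypothesis 1.1-1.4) says that the 12-month mean in each arm "will be compared to baseline scores to assess for significant differences using paired sample t-test". For Hypothesis 1.3 it says "The mean outcomes scores of the mHHS between groups at 12 months will be compared using independent t-tests to assess for significant difference". Its sentence about repeating the analysis names 12 months again; I take 24 months to be meant, in line with Hypothesis 1.4.

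Section III describes two arms only: subjects "will receive conservative physical therapy treatment alone or arthroscopic surgical labral repair and physical therapy". On crossover, Section VIII says "The treatment schema allows for subjects in the non-surgical arm (physical therapy alone) to cross over to the surgical treatment group at any time", with official crossover at 6 weeks after enrolment; Section IV gives the same 6-week limit. For Hypotheses 1.1 to 1.4 the plan names no analysis population and no rule for crossovers. In the power section only Hypothesis 1.5 is marked as a non-crossover analysis. Specific Aim 4 analyses crossovers but does not say whether they leave Aim 1.

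**The concern.** The wording is causal and the test is uncontrolled. A paired t-test against baseline asks whether the mean score moved, not why. Four features of this design stand between a movement and the treatment.

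- Subjects enter because a surgeon judges them symptomatic. Natural course and regression to the mean can shift the mean in either arm, and no untreated arm measures that shift.
- The surgical arm receives surgery and physical therapy, so Hypothesis 1.2 cannot isolate labral repair.
- Physical therapy subjects may have surgery long before 12 months. If they are kept in the analysis of Hypothesis 1.1, the change includes surgery. If they are dropped, those who did poorly are preferentially removed, because failing the advancement criteria is itself a trigger for possible crossover (Section IV).
- Both hypotheses speak of a difference without direction, so a significant worsening would also satisfy them.

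At stake is what the trial may conclude. If Hypothesis 1.3 is not significant and 1.1 and 1.2 both are, the plan as written allows both treatments to be declared effective, although neither has been compared with no treatment.

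**Working it through.** **Inputs from the documents.** Section V (Power Analysis): 35 subjects per arm, a 10-point mHHS difference, 80% power, 5% significance, one-sided independent t-test. No SD is printed, and no significance level or sidedness is stated for the paired tests.

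**The plan's own figure.** Without an SD, 35 per arm cannot be reproduced, only inverted. By the normal formula, SD = 10 × √(35/2) / (1.645 + 0.842) = 41.83 / 2.487 = 16.8. The exact t calculation gives 16.7, which I use. A two-sided test would imply about 14.9 (41.83 / 2.802). The 35 applies to the between-arm test; the paired tests have no power calculation of their own.

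**Assumptions for the illustration.** SD 16.7 at both times; baseline-to-12-month correlation r from 0.3 to 0.7; n = 35; two-sided 5%; no treatment effect at all, only a mean drift.

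**Step 1: SD of change and smallest significant change.** SD of change = SD × √(2(1 − r)). Smallest significant mean change = 2.032 × SD of change / √35.

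| r | SD of change | Smallest significant change |
|---|---|---|
| 0.3 | 19.8 | 6.8 points |
| 0.5 | 16.7 | 5.7 points |
| 0.7 | 12.9 | 4.4 points |

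All three lie below the 10 points that the plan treats as the difference to detect.

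**Step 2: chance of P<0.05 from drift alone** (noncentral t, 34 df, noncentrality = drift × √35 / SD of change).

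| Drift (points) | r = 0.3 | r = 0.5 | r = 0.7 |
|---|---|---|---|
| 0 | 5% | 5% | 5% |
| 2 | 9% | 11% | 14% |
| 5 | 31% | 41% | 60% |
| 7 | 53% | 67% | 88% |
| 10 | 83% | 93% | 99% |

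**Step 3: contrast with the randomised comparison.** Drift common to both arms adds the same amount to each 12-month mean and cancels in the difference. In simulation at r = 0.5 with no treatment effect, both paired tests were significant together in about 0.2%, 16% and 86% of trials at drifts of 0, 5 and 10 points. The between-arm test on change stayed near 5% at all three.

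**Step 4: crossover.** If crossovers stay in the physical therapy arm, their contribution to its mean change is the crossover proportion times their extra gain. With 30% crossing over and 10 extra points (both assumed), that is 0.30 × 10 = 3 points, which as a simple shift is significant in about 14–27% of trials for r 0.3 to 0.7. At r = 0.5 and SD 16.8, 30% × 20 points = 6 points gives about 44%, and 50% × 20 points = 10 points gives about 84%.

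**The case against.** The best defence is that Aim 1 is comparative, Hypothesis 1.3 tests it between randomised arms, and the sample size rests on that test. On this view 1.1 and 1.2 are supporting description. That stands as far as it goes: common drift leaves Hypothesis 1.3 intact. But 1.1 and 1.2 are written as formal hypotheses with causal wording and a significance test, repeated under 1.4, so the plan does not treat them as description.

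It can also be said that a 95% confidence interval shows whether zero is excluded, so removing the P value changes little. Numerically that is right. The gain lies in the wording and in stating which comparison carries the conclusion.

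Three stronger readings are tempting, and the documents do not support them.

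- A reader might infer that the paired tests would be significant from natural course alone. The documents give no natural-course change, SD or correlation, and the chance runs from 5% to 99% across the values above. Nor is the direction settled: subjects are 40 or older, chosen partly for likely undetected osteoarthritis, and there is no mHHS entry threshold. Decline is possible, and the size of any regression to the mean is unknown.
- A reader might infer that crossover surgery alone would make the physical therapy test significant. No crossover rate is given, this route needs crossovers to be kept in the arm, and a 3-point contribution usually falls short.
- A reader might take the aim to "increase the use of conservative therapy (if validated" as intent to validate therapy by within-arm tests. That sentence starts from surgery being shown to offer little or no benefit, and the rest of the paragraph is also comparative.

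**Conclusion.** The point holds as a limit on interpretation. Hypotheses 1.1 and 1.2, and their repeats under 1.4, make causal claims that within-arm paired tests without an untreated arm cannot support. This rests on the design and the wording and needs no numerical assumption.

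The size is illustrative. Non-treatment drift could give P<0.05 in about 9–14% of trials at 2 points and 83–99% at 10 points. The SD of 16.7 is back-solved, and the correlations, drifts and two-sided 5% level are assumed; an SD of 14.9 would raise the percentages (37–70% at 5 points, against 31–60%). The randomised comparison is not inflated by drift common to both arms. This is a low-severity matter of wording and reporting, worth correcting because it governs what the trial may claim.

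**What to change.** In Section II, restate Hypotheses 1.1 and 1.2 and their 24-month repeats in 1.4 as descriptive objectives: mean mHHS change from baseline with a 95% confidence interval for each randomised arm. Remove the causal wording. In Section V, delete the paired t-tests and their P values, and state that crossovers are kept in the arm to which they were randomised. Describe the surgical-arm change as that of surgery plus physical therapy.

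Add one sentence saying that treatment-effect conclusions rest only on the between-arm difference, with its confidence interval, for Hypothesis 1.3 and its 24-month repeat. With crossovers kept as randomised, that difference is the effect of being assigned to one strategy or the other, and the report should say so.

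The cost is a few sentences and the removal of the paired tests; no new data, visits or subjects are needed. The downside is that the trial gives up any standalone claim that physical therapy, or surgery, is effective in its own right.

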We plan to track the effects of OA on outcomes through identification and localization of OA at the time of arthroscopy using a mapping technique (see diagram). After complete visualization of the intra-articular space, as is standard practice in hip arthroscopy, classification of any existing osteoarthritis will be done according to the Outerbridge grading scale. Using this system, we are able to categorically group subjects based on location and severity of disease. If multiple lesions are present, subjects will be characterized by the most severe grade. Furthermore, based on the data gathered through meeting hypotheses 1.1-1.4, we will subdivide primary outcome scores into four categories.⁶⁰ Category I, excellent outcomes (mHHS ≥ 90); Category II, good outcomes (mHHS ≥ 80); Category III, fair outcomes (mHHS ≥ 70), and Category IV, poor outcomes (mHHS < 70). The likelihood of outcomes based on Outerbridge grading and outcome category will be determined through odds ratios. Analysis will be carried out using Chi-squared tests. Significance is set at $P < 0.05$. Linear regression analysis will be performed to detect if any relationship exists between the severity of osteoarthritis and short-term outcome scoring.

Hypothesis 3.1:

This is an exploratory hypothesis whose assessment will no influence the other data sets. Prior work by other groups has demonstrated that evaluation of arthritic burden by conventional measures (Kellgren-Lawrence and Tonnis grading) are not indicative of the severity of arthritis found at the time of arthroscopy.⁵⁸ We will explore this phenomenon in our own cohort of subjects, specifically those in the surgical group and report our findings. We will correlate our findings for significance.

Power Analysis:

Specific Aim 1, Hypotheses 1.1-1.4: *To evaluate if physical therapy alone or arthroscopic labral repair and physical therapy is of greater benefit to patients presenting at age 40 with tears of the acetabular labrum.*

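### Hypothesis 1.5 would read a non-significant within-group test as durability of the physical therapy response; it needs a confidence interval and a justified margin

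*Combined protocol and SAP*

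**What the plan says.** Section II (Specific Aims) states Hypothesis 1.5 as a prediction of no difference: "Functional outcome scores collected at the completion of PT will not significantly differ from those collected at 12 and 24 months". The comparison is within one group and extends to later follow-up. The Power Analysis in Section V gives the method: "Testing of hypothesis 1.5 will be an intragroup analysis looking for a significant difference in outcome measures", from the end of PT to 12 and 24 months, in subjects who have not crossed over. It also gives the use: "The purpose is to determine the short-term durability of the response to PT, if one is found".

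Two other hypotheses in Section II are worded as nulls.
- Hypothesis 4.2: "Baseline scores on outcome measures of those subjects crossing over will not differ significantly from those obtained at the time of crossover". Section V describes no analysis for Aim 4.
- Hypothesis 3.1: "Tonnis grading and Kellgren-Lawrence grading on plain radiography are not predictive of the severity of arthritis at the time of arthroscopy". Section V says "We will correlate our findings for significance", in the surgical group. Aim 3 is labelled exploratory, and the Power Analysis adds that "we recognize that we may be underpowered for the definitive analyses of our radiographic correlation hypotheses".

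None of the three has an equivalence or non-inferiority margin, a confidence-interval rule or a smallest relevant correlation. The only threshold on the mHHS is "a 10 point or greater difference on the mHHS as significant". It belongs to the between-arm comparison, which is also the only comparison that the 35 per arm is calculated for.

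**The concern.** A test built to find a difference controls the risk of claiming one that is absent. It does not control the risk of claiming that nothing changed when something did. Under Hypothesis 1.5 as written, P>0.05 fulfils the prediction and so becomes the evidence for durability, although P>0.05 also results from too few subjects.

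The setting makes this matter. The analysis uses a subset of one arm, and that subset shrinks with each crossover and each missing survey. The Power Analysis reports that only 31 of 47 patients past two years had yielded data. Under the current rule, each lost subject makes the prediction easier to fulfil.

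At stake is a claim that the benefit of PT lasts. Section I (Implications) expects the trial to inform recommendations on conservative treatment, and a durability claim would feed directly into that.

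**Working it through.** **Inputs from the plan (Section V, Power Analysis).** 35 subjects per arm, a 10-point mHHS difference, one-sided 5%, 80% power, 122 enrolled. The SD is not stated.

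**Assumptions.** Within-person correlation ρ of 0.5 to 0.7 (wider range 0.3 to 0.7); SD range 15 to 20; a two-sided 5% paired t-test, since the plan names no test for Hypothesis 1.5; 25 pairs as an illustrative reduced set. The 5-point fall is also illustrative, at half of the plan's 10 points.

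**Step 1: the plan's figure.** It cannot be checked directly without the SD, so it is solved backwards. Normal approximation: SD = 10 / [(1.645 + 0.842) × √(2/35)] = 10 / 0.594 = 16.8. The exact t-test gives 16.66, used below.

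**Step 2: Hypothesis 1.5, chance of a non-significant result.** SD of change = SD × √(2(1 − ρ)), which is 16.66 at ρ = 0.5 and 16.66 × 0.775 = 12.90 at ρ = 0.7. SE = SD of change / √n. Noncentrality = true fall / SE. The miss rate is the noncentral-t probability between the two critical values.

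| Pairs | ρ | SE | Critical t | 5-point fall missed | 10-point fall missed |
|---|---|---|---|---|---|
| 35 | 0.5 | 2.82 | 2.03 | 59% | 7% |
| 35 | 0.7 | 2.18 | 2.03 | 39% | 1% |
| 25 | 0.5 | 3.33 | 2.06 | 70% | 18% |
| 25 | 0.7 | 2.58 | 2.06 | 54% | 4% |

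Over SD 15 to 20 and ρ 0.3 to 0.7, with 35 pairs, the 5-point miss rate runs from about 30% to 77% and the 10-point rate from 0% to 32%.

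**Step 3: would a 10-point margin cure this?** Suppose durability is claimed when the lower 95% limit is above −10.
- If the true change is zero, 25 pairs give 82-96% power.
- If the true change is −5, the claim would still be made in 41-61% of trials with 35 pairs, against 39-59% non-significant now: no improvement. With 25 pairs it would be 30-46%, against 54-70% now.
- With a 5-point margin and no true change, the distance from truth to margin is again 5 points, so power is the same 41-61% with 35 pairs. For 80% power, about 91 PT-only subjects are needed at SD 16.8 and ρ = 0.5 (45 to 178 over the wider range). A 10-point margin needs about 25 (13 to 46).

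**Step 4: Hypothesis 4.2.** The number of crossovers is not given. With an assumed 10, a true 10-point change would be missed in 41-60% of trials (32-78% over the wider range). With 20 it is about 29% at SD 16.8 and ρ = 0.5 (5-57% over the wider range).

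**Step 5: Hypothesis 3.1.** The relevant number is subjects operated on, not 2-year survey completers. Under equal allocation (assumed) that is at most 122 / 2 = 61, less any not operated on or removed for unexpected pathology. With the Fisher z approximation, the 95% limits at an observed r of 0 are ± tanh(1.96 / √(n − 3)): ±0.25 at 61 and ±0.33 at 35. A true r of 0.3 is missed in 35% of trials at 61 and 58% at 35; a true r of 0.4 in 10% and 33%.

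**The case against.** The best defence is that these are not the primary comparison, and that with 35 pairs a fall as large as the plan's only threshold would usually be detected. That stands, and it limits the size of the problem. It does not make a non-significant result evidence of durability, and the plan does not say that losses below 10 points are unimportant.

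Several stronger readings are tempting, and the documents do not support them.
- A reader might put Hypothesis 3.1 on the same footing as 1.5. But Aim 3 is exploratory, is said not to affect the other data, and is disclosed as possibly underpowered.
- A reader might use 35 for Hypothesis 3.1. That is the completer target. Pre-operative radiographs and arthroscopic grade do not depend on survey return, so up to about 61 may be available.
- A reader might infer that the plan will test Hypothesis 4.2 and accept P>0.05. No test is specified, so that criterion rests on the hypothesis wording alone.
- A reader might say that missing surveys help all three hypotheses. This applies to 1.5. It does not apply to 3.1, nor clearly to 4.2, whose scores are taken at baseline and at crossover.
- A reader might treat 10 points as the plan's own margin for durability. It is a between-arm superiority difference, not a stated tolerable loss within a person.

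**Conclusion.** The concern holds for Hypothesis 1.5. A no-difference prediction, a test that looks for a difference, a stated purpose of judging durability and no margin together let P>0.05 stand as evidence that the response lasts. That fault of inference depends on no assumed number. Its size does: the miss rates rest on the back-solved SD and the assumed correlations, and they show a substantial risk for losses of about 5 points, with a much smaller one at 10 points when 35 pairs are available.

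For Hypothesis 4.2 the point is about wording and an unspecified analysis. For Hypothesis 3.1 it is minor. The between-arm primary comparison is not affected. This should be changed, but it does not threaten the trial's main result.

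**What to change.** - **Hypothesis 1.5.** Report the mean mHHS change from PT completion to 12 and to 24 months with its 95% confidence interval and the number of pairs. Claim durability only if the lower limit excludes a pre-specified loss, with the reason for that margin stated. The 10-point between-arm difference is at most an upper bound for it. Report the interval whether or not the claim is met, so that the loss not ruled out is visible.
- **Hypothesis 4.2.** Specify the analysis: the change from baseline to crossover with its confidence interval. Draw no conclusion of no change from P>0.05.
- **Hypothesis 3.1.** Report the rank correlation with its 95% confidence interval and the number operated on. Draw no conclusion that the grades are not predictive from P>0.05.

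The cost is wording only, with the same data. The downside is that a margin well below 10 points may leave Hypothesis 1.5 inconclusive at the planned size, and that Hypothesis 4.2 will often be inconclusive with few crossovers. That is an accurate account of what such data can show.
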